## 8.10 Inclusion/Exclusion Criteria

Subjects' eligibility for the clinical trial will be checked during screening and re-checked at Visit 1 before randomisation (when results of laboratory test at screening are available). After results of laboratory test at Visit 1 becomes available and if any clinically significant abnormality which meets exclusion criteria is found, the subject will be withdrawn from the trial (see section 7.7).

## 8.11 Randomisation

Subjects will be randomised at Visit 1 when all inclusion/exclusion criteria are satisfied, as specified in section 10.6.

## 8.12 Investigator's Assessment of Target Lesion

The (sub)investigator must make the following assessments of the target lesion. All assessments for a subject should be made by the same (sub)investigator. In case the same (sub)investigator is not able to assess the same subject, measures should be taken at the site ensure consistent assessments by the (sub)investigators.

### Severity of clinical signs of target lesion

The severity will be recorded for each of the signs of redness, thickness and scaliness at Visits 1-4, according to the 9-point scales below:

#### Redness

0	=	none (no erythema)
0.5*		
1	=	slight (faint erythema, pink to very light red)
1.5*		
2	=	mild (definite light red erythema)

2.5*		
3	=	moderate (dark red erythema)
3.5*		
4	=	severe (very dark red erythema)
Thickness		
0	=	none (no plaque elevation)
0.5*		
1	=	slight (slight, barely perceptible elevation)
1.5*		
2	=	mild (definite elevation but not thick)
2.5*		
3	=	moderate (definite elevation, thick plaque with sharp edge)
3.5*		
4	=	severe (very thick plaque with sharp edge)
Scaliness		
0	=	none (no scaling)
0.5*		
1	=	slight (sparse, fine scale, lesions only partially covered)
1.5*		
2	=	mild (coarser scales, most of lesions covered)
2.5*		
3	=	moderate (entire lesion covered with coarse scales)
3.5*		
4	=	severe (very thick coarse scales, possibly fissured)

\* intermediate intervals (0.5, 1.5, 2.5, 3.5) are to serve as mid-points between the defined grades (0, 1, 2, 3, 4). See '[Appendix 9: Descriptors for intermediate intervals in severity score of clinical signs of target lesion](#)' which shows descriptors for the intermediate intervals for the purposes of data coding.

#### General change in target lesion

At Visits 2-4, the general change in the target lesion from Visit 1 will be recorded according to the 5-point scale below.

Markedly improved	+++	A very definite improvement (approx. 75% or more)
Moderately improved	++	A definite improvement (approx. 50%)
Slightly improved	+	Some definite improvement (approx. 25%), however, significant signs remain
Unchanged	+/-	No change
Aggravated	-	Worsened

### 8.13 Subject's Assessments

At Visit 4, the subject will make the following assessments. If a subject withdraws from or completes the trial at Visits 2 or 3, the assessment should be done at this time in lieu of the one at Visit 4.

Time spent for application, scored as less time, slightly less time, unchanged, slightly more time, more time as compared to previous topical treatments.

Ease of application, scored as very easy, easy, difficult, very difficult as compared to previous topical treatments.

### 8.14 Supply/Return of IMP and Compliance

Refer to sections [10.7.1](#) and [10.7.3](#)

## 9 Adverse Events

- AEs and SAEs are defined in [Appendix 3: Definitions of Adverse Events and Serious Adverse Events](#).
- Classification of AEs in terms of severity, causality and outcome are defined in [Appendix 4: Classification of Adverse Events](#).

### 9.1 Collection of Adverse Events

AEs must be collected from the signing of the informed consent form until the last trial visit.

AEs must be assessed by (sub) investigators who are medically qualified.

At all visits, the (sub)investigator should ask the subject a non-leading question to the effect of: "How have you felt since I saw you last?" No specific symptoms should be asked for. It is important that the (sub)investigator also observes the subject for any changes not reported by the subject and records these changes.

If there are no AEs to record, no further questions should be asked and “NO” should be ticked in the eCRF. In case there are one or more AEs to record, “YES” should be ticked.

## 9.2 Reporting of Adverse Events in the eCRF

AEs reported by the subject or observed by the (sub)investigator must be recorded on the AE form of the eCRF and should be described in the following manner:

The *AE term* will be in precise English medical terminology (i.e. not necessarily the exact words used by the subject). Whenever possible, a specific diagnosis should be stated (e.g. allergic contact dermatitis).

For cutaneous AEs, the *location* must be part of the AE description and will be described as either:

- lesional/perilesional ( $\leq 2$  cm from the border of lesion(s) treated with IMP), or
- distant ( $>2$  cm from the lesion border)

The *duration* of the AE must be reported as the start date and stop date of the event (it will also be recorded if the event is ongoing). In addition, it must be recorded whether the AE started prior to start of trial medication.

AEs must be classified in terms of severity, causality and outcome according to the definitions in [Appendix 4: Classification of Adverse Events](#).

### 9.2.1 Actions Taken as a Consequence of an AE

*Action taken with trial treatment:* Any action taken with trial medication as a consequence of the AE must be recorded (dose not changed, dose reduced, dose increased, drug interrupted, drug withdrawn, not applicable, unknown).

*Other action taken:* Any other action taken as a result of the AE must be recorded (none, concomitant medication, concurrent procedure).

*Withdrawn due to AE:* It must be recorded whether the AE leads to withdrawal from the trial.

## 9.3 Other Events to be Reported

### 9.3.1 Pregnancy

Any pregnancy occurring after first exposure to IMP and until the subject has completed the trial must be reported to LEO Pharma K.K. within 24 hours of first knowledge using the (paper) Pregnancy Form (Part I). All such pregnancies must be followed up until delivery or

termination and final outcome must be reported on the (paper) Pregnancy Form (Part II) within 24 hours of first knowledge.

The completed Pregnancy Forms must be faxed or scanned and e-mailed to LEO Pharma K.K. using the following fax number or e-mail address:

[contact]

E-mail address: [contact]

Please also confer with section [7.7](#), Withdrawal Criteria.

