### Treatment period

The treatment period will last for up to 4 weeks. Trial visits will be performed on Day 1 (Visit 1) and after 1, 2 and 4 weeks (Visits 2, 3 and 4). Visit 2 and Visit 3 should be performed within  $\pm 1$  day of the scheduled time (Day 7-9 and Day 14-16, respectively), and Visit 4 should be performed within  $\pm 2$  days of the scheduled time (Day 27-31), in all cases relative to Visit 1. If they are outside this window, the (sub)investigator should record the reason in the patient's medical record.

At Visit 1, subjects will be randomised to receive treatment with either LEO 90100 foam or Dovobet® ointment. Trial medication will be applied once daily to psoriasis on a target lesion of the body. After this application on the target lesion, subjects will also apply trial medication to any other areas of psoriasis, excluding psoriasis on the scalp, face, genitals, and skin folds (axillae, groin, infra-mammary, those around the buttocks and the perianal area).

On the assessment day of the target lesion (Visit 1, Visit 2, Visit 3 and Visit 4), subject should not apply any topical treatment including emollients on the target lesion before the visit. Showering or bathing should also be avoided.

Subjects with the target lesion achieving 'substantial resolution', as defined in section 5, before the end of 4 weeks' treatment will complete the trial at this time (although they will still be required to attend the follow-up visit up to 14 days later, if applicable; see below).

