### 7.2 Inclusion Criteria

1. Signed and dated informed consent has been obtained prior to any protocol-related procedures.
2. Japanese subjects
3. Aged 20 years or above
4. Clinical diagnosis of psoriasis vulgaris amenable to topical treatment of less than or equal to 30% BSA (excluding psoriasis on the face/genitals/skin folds)
5. A target psoriasis lesion on the body, which is of a minimum size of 10 cm^2 and scoring at least 2 (mild) for each of the clinical signs (redness, thickness and scaliness). The lesion must not be on the scalp, face, genitals or skin folds.
6. Females of childbearing potential must have a negative result for a urine pregnancy test at Day 1 (Visit 1) and must agree to use an adequate method of birth control, as judged by the (sub)investigator, during the trial. The contraceptive method should have started an adequate amount of time before the pregnancy test, which is dependent on the particular method used and as judged by the (sub)investigator, and must continue for at least 1 week after the last application of trial medication. A female is defined as not of child-bearing potential if she is postmenopausal (12 months with no menses without an alternative medical cause) or surgically sterile (tubal ligation/section, hysterectomy or bilateral ovariectomy).
7. Able to communicate with the (sub)investigator and understand and comply with the requirements of the trial.

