## 7.7 Withdrawal Criteria

Subjects **may** withdraw from the trial for any of the following reasons:

1. *Unacceptable treatment efficacy*: the (sub)investigator is free to withdraw the subject at any time based on a medical judgement.
2. *Unacceptable AEs*: any AE that the (sub)investigator or the subject considers unacceptable.
3. *Exclusion criteria*: any exclusion criteria which emerge/become apparent during the subject’s participation in the clinical trial.
4. *Voluntary withdrawal*: subjects are free to withdraw from the clinical trial at any time and for any reason.
5. *Other reasons*: other reasons than stated above which require the subject to (be) withdraw(n) should be specified.

Subjects **must** be withdrawn if they are found to have become pregnant.

Subjects with the target lesion achieving ‘substantial resolution’, as defined in section 5, before the end of 4 weeks’ treatment will complete the trial at this time (although will still be required to attend the follow-up visit up to 14 days later if applicable)

Subjects who are discovered, after randomisation, not to have fulfilled all inclusion/exclusion criteria at the time of randomisation, should be withdrawn from treatment unless the (sub)investigator finds withdrawal inappropriate, based on clinical and ethical evaluation.

Reason(s) for withdrawal will be recorded in the eCRF. Withdrawn subjects will not be substituted.

Completion of trial is defined as:

A subject who attends Visit 4 on Day 29 or later

or

A subject who attends Visit 4 earlier than Day 29, but the reason for attending earlier than Day 29 is not because (a) the (sub)investigator wishes to withdraw the subject, or (b) the subject wishes to withdraw

or

Subjects with the target lesion achieving ‘substantial resolution’, as defined in section 5, before the end of 4 weeks treatment.

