## 8.9 Pregnancy Test

A urine pregnancy test will be performed at the trial site at Visit 1 (prior to randomisation) and Visit 4 in female subjects of child-bearing potential. If a subject withdraws from or completes the trial at Visits 2 or 3, the test should be done at this time in lieu of the one at Visit 4. The test kits will be provided by the central laboratory.

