## 6. Use during pregnancy, delivery and lactation

### (1) Pregnant women, etc.:

It is desirable not to use this medication in pregnant women or women who may be pregnant [safety in application during pregnancy has not been established. It has been reported that calcipotriol is transferred to fetuses via the placenta in an animal experiment (rats). It has been reported that betamethasone has teratogenic action in animal studies (mice, rats, rabbits)] .

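### Pregnancy reporting ends at trial completion, but contraception is required for at least a further week, so conceptions in the last 6–7 days of that period fall outside mandatory reporting

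*Protocol*

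**What the plan says.** Section 9.3.1 defines what must be reported: "Any pregnancy occurring after first exposure to IMP and until the subject has completed the trial must be reported". The report is due "within 24 hours of first knowledge using the (paper) Pregnancy Form (Part I" of the form), and each such pregnancy is followed to delivery or termination.

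Inclusion criterion 6 (section 7.2) says of contraception that it "must continue for at least 1 week after the last application of trial medication".

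Testing is set out in section 8.9: "A urine pregnancy test will be performed at the trial site at Visit 1 (prior to randomisation) and Visit 4". For early exits, "If a subject withdraws from or completes the trial at Visits 2 or 3, the test should be done at this time". The schedule in section 8.1 also allows a test at an unscheduled or early-withdrawal visit, but none at follow-up. Under section 6.1, follow-up takes place only for a related adverse event or an SAE present at the last visit.

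Completion is defined twice. Section 7.7 begins with "A subject who attends Visit 4 on Day 29 or later" and adds attendance before Day 29 for reasons other than withdrawal, and early substantial resolution of the target lesion. Section 6.5 requires all periods of the trial, including the last visit, to be finished, or early substantial resolution.

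The package insert in Appendix 2 states that safety in pregnancy has not been established. It reports placental transfer of calcipotriol in rats, and for the corticosteroid: "It has been reported that betamethasone has teratogenic action in animal studies".

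**The concern.** The protocol asks women to avoid conceiving for at least a week after the last application, but stops requiring reports of conception about a week earlier. A pregnancy that begins in that week is one the contraception rule was meant to prevent. Section 9.3.1 nevertheless does not require it to be reported or followed to outcome.

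Three features of the wording add to this:

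- It does not say whether *occurring* refers to conception or to diagnosis. It cross-refers to section 7.7, where the trigger for withdrawal is being found to be pregnant, so a site could take the diagnostic reading.
- A subject who withdraws never completes, so the window has no clear end for her.
- Section 9.4.1 tells sites to report SAEs that they learn of after the trial. Section 9.3.1 has no matching provision for pregnancy.

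At stake is safety information on a formulation being developed for approval in Japan. Few pregnancies would be expected in a 180-subject, 4-week trial, so losing even one report would matter.

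**Working it through.** The plan gives no figure of its own to reproduce. The check is day arithmetic plus a comparison of the relevant sections.

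**1. The gap between the two windows.** Inputs:

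- Visit 4 is planned for Day 29, within 2 "days of the scheduled time (Day 27-31), in all cases relative to Visit 1" (section 6.1).
- Subjects should not treat the target lesion before the visit on assessment days (section 6.1). The last application is therefore taken as the day before the exit visit, with the same day as the upper case.
- Contraception lasts at least 7 days after the last application (section 7.2).
- Reporting is taken to end at the exit visit (section 7.7).

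Formulas: contraception end = last application + 7; gap = contraception end − exit visit day; share = gap ÷ contraception end (days from first exposure on Day 1).

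| Exit visit | Last application | Contraception to at least | Gap | Share outside reporting |
|---|---|---|---|---|
| Visit 4, Day 29 | Day 28 | Day 35 | 6 days | 6/35 = 17% |
| Visit 4, Day 29 | Day 29 | Day 36 | 7 days | 7/36 = 19% |
| Visit 3, Day 15 | Day 14 | Day 21 | 6 days | 6/21 = 29% |
| Visit 2, Day 8 | Day 7 | Day 14 | 6 days | 6/14 = 43% |

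Counting simply 28 treatment days plus 7, with 28 days reported, gives 7/35 = 20%. The range for a subject treated for 4 weeks is therefore about 17–20%. Across the Visit 4 window of Days 27–31, the contraception period ends between Day 33 (26 + 7) and Day 38 (31 + 7), and the gap stays at 6–7 days.

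**2. The effect of the second completion definition.** Under section 6.5, a subject with a follow-up visit may not have completed until that visit. This could be as late as Day 29 + 14 = Day 43, past the end of the contraception period at Day 35–36. The gap would then close for her. That visit is conditional, however. Section 6.1 also says that a subject who clears early completes at that time even if a follow-up visit is still due, so the extension does not clearly reach early completers.

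**3. What the exit test can show.** The documents give no lag from conception to a positive urine test. Assume 10–14 days, with 21 days as a wider case. The last detectable conception day is the test day minus the lag.

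- Day 29 test: 29 − 10 = Day 19; 29 − 14 = Day 15; 29 − 21 = Day 8. With the last application on Day 28, the final 9, 13 or 20 treatment days respectively are not covered.
- Day 15 test: 15 − 10 = Day 5; 15 − 14 = Day 1.
- Day 8 test: 8 − 10 = −2, before first exposure, so no on-treatment conception would be visible.

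Late on-treatment conceptions will thus often come to light only after exit, which is why the wording on late knowledge matters.

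**4. Which pregnancies the text covers.**

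| Pregnancy | Position under section 9.3.1 |
|---|---|
| Conceived and diagnosed before completion | Reportable |
| Conceived before completion, recognised later | Reportable on the natural reading; not if *occurring* is read as diagnosed |
| Conceived after completion, within the contraception period | Not reportable |
| Conceived after withdrawal | No clear end date |

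**The case against.** The strongest objection concerns a reading that the two windows may invite: that pregnancies exposed late in treatment are neither detected nor reportable. The documents do not support this. A Week 4 conception occurs before completion, and the 24-hour clock starts at first knowledge with no cut-off for when that knowledge arises. On the natural reading it must be reported and followed. Nor is detection absent, since the exit test can show conceptions from the earlier part of treatment. This part of the objection stands.

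A reader might also take the undetectable share at exit as the size of the reporting gap. With a 10–14 day lag, that share is 35 − 19 = 16 to 35 − 15 = 20 of 35 days, or 46–57%. It measures test timing, includes days after the test, rests on an assumed lag, and would be unchanged by a better reporting sentence. It is not the size of this point.

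It can further be said that the protocol never calls the contraception period a risk or reporting period, and that a contraceptive buffer may reasonably outlast a reporting window. The first part is correct: the link is an inference. But no reason is given for the difference, and the uncovered days are ones on which the protocol itself still wants conception avoided.

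There are also partial safeguards. Pregnant women and those wishing to conceive are excluded, and a negative test is required at Visit 1. A congenital anomaly is an SAE (Appendix 3) and is reportable after the trial if the investigator learns of it (section 9.4.1). These reduce the consequence without closing the gap: pregnancy itself is not on the SAE list, late SAEs are not sought, and an anomaly would be captured only after the harm.

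**Conclusion.** The point holds in a limited form. Conceptions after completion but within the required contraception period are excluded from mandatory reporting by the stated rule. The gap is 6–7 days, about 17–20% of 35 days for a subject treated for 4 weeks and a larger share for early completers. This assumes that the last application falls on the day of the exit visit or the day before, and that completion follows section 7.7. Subjects whose completion is delayed by a follow-up visit under section 6.5 may be covered.

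Pregnancies conceived on treatment and recognised after exit are reportable on the natural reading, but the wording leaves room for a site to decide otherwise. The position of withdrawn subjects is unclear. The exit test may miss recent conceptions; how many days it misses depends on the assumed lag.

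Nothing here affects the sample size, the endpoints or the efficacy analysis. It is a cheap improvement to safety capture.

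**What to change.** Reconcile section 9.3.1 with inclusion criterion 6 and with the completion definitions in sections 6.5 and 7.7. In section 9.3.1, state that any pregnancy with an estimated conception date from first exposure to the end of the contraception period already required by criterion 6 is to be reported and followed to outcome whenever the site learns of it, including for early completers and withdrawn subjects. This settles the meaning of *occurring*, removes the dependence on which completion definition applies, and supplies the late-knowledge provision that section 9.4.1 already gives for SAEs.

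At exit, ask women of child-bearing potential to tell the site of any such pregnancy.

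The cost is one sentence in section 9.3.1, one line in the subject instructions and an occasional form filed after a subject has left. No visit, test, contraception requirement or treatment rule changes. The exit test's limits remain; the exit request is what bears on pregnancies recognised later.

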### 9.3.2 Overdose

An overdose is defined as a subject receiving a quantity of IMP per administration or per week which is in excess of that specified in this protocol. An overdose is either accidental or intentional.

For Dovobet® ointment and LEO 90100 foam, overdose is defined as application of >90g/week, based upon the package insert of the already marketed Dovobet® ointment.

The term ‘overdose’ including a specification of why it occurred (accidental or intentional) must be recorded on the AE form of the eCRF. In addition, AEs originating from overdose must be recorded as separate events. If the AE originating from the overdose qualifies as an SAE, expedited reporting is required (Section [9.4](#)).

If the overdose is accidental and due to a device deficiency, the device deficiency must be reported as a product complaint as described in Section [10.9](#).

### 9.3.3 Medication Error

Medication error refers to any unintentional error in the dispensing or administration of a medicinal product while in the control of the (sub)investigator or subject. Broadly, medication errors fall into four categories: wrong medication, wrong dose (including strength, form, concentration, amount), wrong route of administration or wrong subject.

The medication error must be documented on the AE form of the eCRF. In addition, AEs originating from a medication error must be documented on a separate line specifying the category of error (see definitions above).

If the medication error is due to a device deficiency, the device deficiency must be reported as a product complaint as described in Section [10.9](#).

### 9.3.4 Misuse

Misuse refers to situations where the medicinal product is intentionally and inappropriately used not in accordance with the protocol.

The term 'misuse' must be documented on the AE form of the eCRF. In addition, AEs originating from misuse must be documented on a separate line. If the AE originating from misuse qualifies as an SAE, expedited reporting is required (Section 9.4).

